**LIST OF ABBREVIATIONS**

ABT-450	NS3/NS4A (non-structural protease inhibitor)
ABT-450/r	Ritonavir (pharmacokinetic enhancer)
ABT-267	Ombitasvir (NS5A inhibitor)
ABT-333	Dasabuvir (NS5B non-nucleoside polymerase inhibitor)
AE	Adverse Event
ALT	Alanine aminotransferase (also SGPT)
ANCOVA	Analysis of Covariance
ANOVA	Analysis Of Variance
Anti-HIV Ab	Anti-Human Immunodeficiency Virus Antibody
APRI	Aspartate aminotransferase to Platelet Ratio Index
AUC	Area Under the Curve
β-hCG	beta-human Chorionic Gonadotropin
BMI	Body Mass Index
BP	Blood Pressure
CFR	Code of Federal Regulations
CRO	Contract Research Organization
CYP	Cytochrome P450
CYP2C8	Cytochrome P450 2C8
CYP3A	Cytochrome P450 3A
DAA	Direct-Acting Antiviral
DMC	Data Monitoring Committee
dL	Deciliter
DNA	Deoxyribonucleic Acid
FDA	Food and Drug Administration (United States)
FSH	Follicle-Stimulating Hormone
ECG	Electrocardiogram
FibroScan	A non-invasive ultrasound procedure
eRVR	Extended Rapid Virologic Response
GCP	Good Clinical Practice
g/dl	gram/deciliter
Gr	Grade
Hb	Hemoglobin
HBsAg	Hepatitis B surface Antigen
HBV	Hepatitis B Virus
hCG	Human Chorionic Gonadotropin
HCV	Hepatitis C Virus
HCVAb	Hepatitis C Virus Antibody
HIV	Human Immunodeficiency Virus
HRQoL	Health Related Quality of Life
HT	Height
ICF	Informed Consent Form
ICH	International Conference on Harmonisation
IEC	Independent Ethics Committee
IFN	Interferon
IND	Investigational New Drug (Application)
INR	International Normalized Ratio (of prothrombin time)

IRB	Institutional Review Board
IU	International Unit
IWRS	Interactive Web Response System
kg	kilogram
KPSC	Kaiser Permanente Southern California
L	Liter
LLOQ	Lower Limit of Quantification
mg	milligram
min	minute
mL	milliliter
N	Number
NDC	National Drug Code
P	Pulse Rate
PBO	Placebo
PT	Prothrombin Time
PTT	Partial Thromboplastin Time
PK	Pharmacokinetic
pegIFN	pegylated-interferon
PRO	Patient Reported Outcomes
RBV	Ribavirin
RNA	Ribonucleic Acid
SCPMG	Southern California Permanente Medical Group
SD	Standard Deviation
SOC	Standard Of Care
SOP	Standard Operating Procedure
SVR	Sustained Virologic Response
SVR4	Sustained Virologic Response at 4 Weeks after treatment completion
SVR12	Sustained Virologic Response at 12 Weeks after treatment completion
TSH	Thyroid Stimulating Hormone
WT	Weight (body)
ULN	Upper Limit of Normal

**PROTOCOL SUMMARY**

Title	A Phase IV, Multisite Study of the Treatment of Chronic Hepatitis C Virus Infection Genotype 1 in a Real World Large Health Maintenance Organization: An Evaluation of Real World Sustained Virological Response and Patient Reported Outcomes
Short Title	Real World Study: Genotype 1 Chronic HCV Treatment and Evaluation of Real World SVR and PROs
Protocol Number	IRB 10568
Study Phase	Phase IV
Study Site(s)	Multiple Kaiser Permanente Southern California Medical Centers
Number of Subjects	200
Study Arms	Two study arms 
 
• Genotype 1a: VIEKIRA PAK (ombitasvir, paritaprevir/r, dasabuvir) + RBV (ribavirin)
 
• Genotype 1b: VIEKIRA PAK (ombitasvir, paritaprevir/r, dasabuvir)
 

Indication	Treatment of patients with genotype 1 chronic hepatitis C virus (HCV) infection
Primary Objective	The primary objective of this open label study is to evaluate the rate of sustained virological response rate 12 weeks after completion of treatment (SVR12) with VIEKIRA PAK (ombitasvir, paritaprevir/r, dasabuvir), with or without ribavirin in a large real world setting.
Overview of Study Design	This is a Phase IV, open-label, multi-center study to evaluate the real world sustained virological response rate, subject adherence, and subject reported outcomes during and after treatment of non-cirrhotic genotype 1 chronic hepatitis C subjects aged 18 years and older, with the AbbVie 3 direct-acting antiviral (3-DAA) regimen of VIEKIRA PAK (ombitasvir, paritaprevir/r, dasabuvir), with or without ribavirin. Subjects may be treatment-naïve or treatment experienced with pegylated-interferon based regimens excluding regimens with direct-acting antiviral agents.
Investigational Product Administration	VIEKIRA PAK (ombitasvir, paritaprevir/r, dasabuvir) VIEKIRA PAK is ombitasvir, paritaprevir, ritonavir fixed dose combination tablets copackaged with dasabuvir tablets.  Ombitasvir, paritaprevir, ritonavir fixed dose combination tablet includes a hepatitis C virus NS5A inhibitor (ombitasvir), a hepatitis C virus NS3/4A protease inhibitor (paritaprevir), and a CYP3A inhibitor (ritonavir) that inhibits CYP3A mediated metabolism of paritaprevir, thereby providing increased plasma concentration of paritaprevir. Dasabuvir is a hepatitis C virus non-nucleoside NS5B palm polymerase inhibitor, which is supplied as separate tablets in the copackage. Both tablets are for oral administration.  VIEKIRA PAK is dispensed in a monthly carton for a total of 28 days of therapy. Each monthly carton contains four weekly cartons. Each weekly carton contains seven daily dose packs. Each child resistant daily dose pack contains four tablets: two 12.5/75/50 mg ombitasvir, paritaprevir, ritonavir

	
tablets and two 250 mg dasabuvir tablets, and indicates which tablets need to be taken in the morning and evening. The NDC number is NDC 0074-3093-28.
 
VIEKIRA PAK:
 
 
• Two ombitasvir, paritaprevir, ritonavir tablets once daily (in the morning) with a meal without regard to fat or calorie content and
 
• One dasabuvir tablet twice daily (morning and evening) with a meal without regard to fat or calorie content.
 
 
Ribavirin
 
Ribavirin is a synthetic nucleoside analogue (purine analogue). The chemical name of ribavirin is 1-β-D-ribofuranosyl-1H-1,2,4-triazole-3-carboxamide. Ribavirin capsules USP, 200 mg are white, opaque, hard gelatin capsules imprinted (in blue) RIBAVIRIN over 200 mg on cap and GG 608 on body.
 
RBV (ribavirin): Dosage is based on weight and adjusted for renal impairment subjects.
 
 
• If subject weighs less than or equal to 75 kg, 1000 mg daily in two divided doses with food.
 
• If subject weighs greater than 75 kg, 1200 mg daily in two divided doses with food.
 


Eligibility Criteria
	
Inclusion Criteria
 
 
1. Male or female at least 18 years of age at time of screening.
 
2. Subject voluntarily signed the Informed Consent Form for the study.
 
3. Subject is able to adhere to study visit/ procedure schedule and protocol requirements
 
4. Subject, if female must not use estrogen-containing hormonal contraception including oral, injectable, implantable, patch and ring varieties during study drug treatment
 
5. Subject, if female must meet at least one of the following: 
 
• Subject of childbearing potential must agree to either 
 
○ practice 2 effective contraceptive methods for study duration, starting at the Screening Visit through 30 days after stopping study drug if not receiving ribavirin, 7 months/or as directed by ribavirin label if receiving ribavirin
 
○ practice total abstinence from sexual intercourse (minimum 1 complete menstrual cycle)
 
○ Sexually active with female partner only
 
 
 
• Postmenopausal defined as age appropriate amenorrhea for ≥ 2 years prior to screening and post-menopausal state confirmed by follicle-stimulating hormone (FSH) level
 
• Surgically sterile defined as bilateral tubal ligation or bilateral oophorectomy or hysterectomy
 
• Has male sexual partner with vasectomy
 
 
 

6. Subject, if male, who is not surgically sterile and is sexually active with female partner of childbearing potential must agree to practice 2 effective contraceptive methods for study duration, starting at Screening through 30 days after stopping study drug if not receiving ribavirin, 7 months/or as directed by ribavirin label if receiving ribavirin
7. Subject must have at least one of the following indicators of chronic hepatitis C virus infection prior to study enrollment:
  - Positive anti-HCV antibody or HCV RNA > 10,000 IU/mL at least 6 months before screening, and positive for HCV RNA at the time of screening
  - HCV RNA > 10,000 IU/mL at screening and liver biopsy consistent with chronic HCV infection
  - Credible evidence of chronic hepatitis C as per the investigator and HCV RNA > 10,000 IU/mL at the time of screening.
8. Subject has a screening laboratory result indicating HCV genotype 1-infection. Historical genotype within 6 months of screening may be used at the discretion of the investigator.

Exclusion Criteria

1. Subject declined to sign the Informed Consent Form for the study.
2. Subject, if female is pregnant or is breastfeeding, or if male, with female partner who is currently pregnant.
3. Subject has positive test result for hepatitis B surface antigen or confirmed positive anti-HIV antibody test
4. Subject received study contraindicated medications including but not limited to those listed in [Table 5](#), or medications contraindicated for ritonavir or ribavirin per FDA label prior to study drug administration and unwilling to discontinue prior to starting the study drug. For those that receive ribavirin, contraindicated medications must be discontinued at least 2 weeks or 10 half-lives prior to study drug administration, whichever is longer.
5. Use of known strong inducers of cytochrome P450 3A (CYP3A) or strong inducers of cytochrome P450 2C8 (CYP2C8) or strong inhibitors of CYP2C8 within 2 weeks of the respective medication/supplement prior to initial dose of study drug (see [Table 5](#)).
6. Clinically significant abnormalities or co-morbidities, other than HCV infection that in opinion of the investigator makes subject unsuitable for this study or drug regimen
7. Current enrollment in another interventional clinical study or prior or current use of any investigational or commercially available anti-HCV agents other than interferon or ribavirin including previous exposure to ABT450 (paritaprevir), ABT-267 (ombitasvir) or ABT-333 (dasabuvir) or receipt of any investigational product within 6 weeks prior to study drug administration
8. Prior treatment of chronic HCV infection with a direct acting antiviral agent(s): telaprevir, boceprevir, sofosbuvir, simeprevir, or other direct acting antiviral

	
 
9. History of solid organ transplant
 
10. Screening laboratory analyses shows any of the following abnormal laboratory results: 
 
• Glomerular filtration rate < 30 mL/min as estimated by the Cockcroft-Gault equation
 
• Hemoglobin < 12 gram per deciliter for male
 
• Hemoglobin < 11 gram per deciliter for female
 
 
 
11. Evidence of cirrhosis, documented by one of the following: 
 
• Liver biopsy histologic diagnosis: Metavir Score > 3 (includes 3 - 4 or 3/4) or Ishak score > 4
 
• In the absence of liver biopsy: a FibroScan score ≥ 12.5 kPa
 
• In the absence of a FibroScan: an APRI score > 1.5
 
• In the judgment of the investigator clinical findings are consistent with cirrhosis. In general, a non-cirrhotic result from a Fibroscan will supersede evidence of cirrhosis based on APRI and a liver biopsy not showing cirrhosis will supersede both Fibroscan and APRI
 
 
 
12. History of liver decompensation: ascites noted on a physical exam, imaging or other test; variceal bleeding; hepatic encephalopathy
 
13. Confirmed presence of hepatocellular carcinoma indicated on computed tomography, magnetic resonance, or other imaging techniques within 3 months prior to screening
 
14. HCV genotype performed during screening indicates infection with any genotype other than genotype 1
 
15. Recent history of drug or alcohol abuse that could, in the opinion of the investigator, affect adherence to the study protocol
 

Study Endpoint	
The primary efficacy endpoint is to assess SVR12 in two subgroups of HCV (genotype 1a or 1b). The simple percentage of subjects achieving SVR12 will be calculated and a two-sided 95% confidence interval of the percentage will be computed based on Wilson's score method. We cannot know a priori how the 200 patients will be split into the two subgroups, but we expect each group to have approximately 100 patients (presumably between 80 and 120). Assuming a subgroup size of 100 each, the lower bound of the 95% confidence interval will be within 7 percentage points of the observed SVR12 rate. Once the groups are fixed, the actual lower bound of the 95% confidence interval can be computed.
 
The observed SVR12 rate and confidence interval will be discussed in the context of results from randomized clinical trials, such as the SAPPHIRE-I/II trials and PEARL-II/III/IV trials described in the Background section. While formal statistical inference comparing results of this study to those of the randomized clinical trials will not be conducted, the point estimates and confidence intervals will be compared to assess the degree to which results from the real world setting are similar to or different from those in the randomized clinical trial setting.

	
Results by prior treatment experience and response may be summarized if appropriate, based on the number of subjects enrolled in each subgroup. No subgroup sample size targets have been established.

Statistical Methods	
This is an open label, non-randomized, study with two study arms. Descriptive statistics will be used to describe the observed sustained virological response rate and patient adherence to the treatment regimen. The primary analysis, to evaluate SVR12, will occur after all subjects have completed or prematurely discontinued the study.
 
The intent-to-treat population will consist of all enrolled subjects in this study. The primary efficacy analysis on clinical outcomes will be performed on all subjects in the intent-to-treat population. The modified intent-to-treat population will include all who receive at least one dose of study drug. No data will be imputed for any efficacy or safety analyses except for analyses of the HCV RNA endpoints.
 
HCV RNA values will be selected for the SVR12 analysis based on the defined visit. The visit window for analysis of SVR4 is post-treatment days 2-56, and the visit window for analysis of SVR12 is post-treatment days 57-168. The latest available value within each window will be used to define the SVR 4 or SVR12 result.

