Moreover, patients with compensated cirrhosis who achieve sustained virologic response essentially eliminate their subsequent risk of decompensation, may achieve histologic regression, and decrease their risk of hepatocellular carcinoma by two-thirds. In patients with advanced fibrosis and cirrhosis, viral suppression by more than 4 logs10 with pegylated interferon and ribavirin was associated with marked reduction in death/liver transplantation, and in liver-related morbidity and death.

Combinations of direct-acting antiviral (DAA) agents targeting different steps of viral replication have the potential to significantly improve hepatitis C virus treatment, compared to the current interferon-containing regimens for HCV genotype 1 infection. Combination DAA allows for increased/sustained virologic response rates, elimination of interferon as a component of therapy, increased safety, and tolerability of treatment, shortened duration of therapy and simplifying the treatment algorithm.

Wider application of direct-acting antiviral agent therapy and better responses with combination direct-acting antiviral agent regimen(s) could significantly reduce the public health burden of this disease.

AbbVie's interferon-free regimen for the treatment of chronic hepatitis C virus genotype 1 infection includes three direct-acting antiviral agents targeting different steps in hepatitis C virus

replication: ABT-450 is a nonstructural protein 3/nonstructural protein 4A (NS3/NS4A) protease inhibitor co-administered with a pharmacokinetic (PK) enhancer, ritonavir (ABT-450/r); an NS5A inhibitor ABT-267 (ombitasvir) and ABT-333 (dasabuvir) an NS5B non-nucleoside polymerase inhibitor.

The three direct-acting antiviral (3-DAA) agents regimen has been studied with and without ribavirin in over 2,300 patients in Phase 3 trials across a variety of patient populations including those with compensated cirrhosis. Based on Phase 3 data, the regimen with or without ribavirin appears to be safe, well tolerated, and efficacious in treatment-naïve and treatment-experienced hepatitis C virus genotype 1-infected subjects including those with compensated cirrhosis. The overall efficacy results (intent-to-treat) from the Phase 3 studies are listed in Table 1.

**Table 1 - Combined SVR 12 Rates (Intent-to-treat, missing = failure) from Phase 3 Studies by Subpopulation of Subtype, Prior Treatment History, and Presence or Absence of Cirrhosis**

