In Study M14-002, 305 subjects were randomized and received at least one dose of study drug. The SVR12 rates for treatment-naïve subjects with HCV genotype 1a-infection who received three direct-acting antiviral agents either with or without ribavirin for 12 weeks in Study PEARL-IV were 97.0% and 90.2%, respectively. The SVR12 rate in the 3-DAA arm did not achieve noninferiority to the 3-DAA and ribavirin arm. Virologic failure was noted in 2/100 (2.0%) subjects (on treatment virologic failure: n = 1; relapse: n = 1) in the ribavirin-containing regimen and 16/205 (7.8%) subjects (on treatment virologic failure: n = 6; relapse: n = 10) in the ribavirin-free regimen. The difference between arms demonstrates that ribavirin contributes to the efficacy in genotype 1a-infected patients and suggests that three direct-acting antiviral agents and ribavirin is the optimal regimen for these patients.

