### **8.3.1 Primary Efficacy Endpoint**

The primary efficacy endpoint is to assess SVR12 in two subgroups of HCV (genotype 1a or 1b). The simple percentage of subjects achieving SVR12 will be calculated and a two-sided 95% confidence interval of the percentage will be computed based on Wilson's score method. We cannot know a priori how the 200 patients will be split into the two subgroups, but we expect each group to have approximately 100 patients (presumably between 80 and 120). Assuming a subgroup size of 100 each, the lower bound of the 95% confidence interval will

be within 7 percentage points of the observed SVR12 rate. Once the groups are fixed, the actual lower bound of the 95% confidence interval can be computed.

The observed SVR12 rate and confidence interval will be discussed in the context of results from randomized clinical trials, such as the SAPPHIRE-I/II trials and PEARL-II/III/IV trials described in the Background section. While formal statistical inference comparing results of this study to those of the randomized clinical trials will not be conducted, the point estimates and confidence intervals will be compared to assess the degree to which results from the real world setting are similar to or different from those in the randomized clinical trial setting. Results by prior treatment experience and response may be summarized if appropriate, based on the number of subjects enrolled in each subgroup. No subgroup sample size targets have been established.

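### Is the 7-point precision statement for 100 subjects per genotype group wrong because it names no SVR12 rate?

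*Combined protocol and SAP*

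**What the plan says.** The Study Endpoint entry of the Protocol Summary and section 8.3.1 carry the same text. SVR12 is estimated separately in genotypes 1a and 1b, and "a two-sided 95% confidence interval of the percentage will be computed based on Wilson's score method". The split of the 200 subjects is not known in advance. The plan expects about 100 per group, with a presumed range of 80 to 120. On precision, the Summary states: "Assuming a subgroup size of 100 each, the lower bound of the 95% confidence interval will be within 7 percentage points of the observed" proportion with SVR12. Section 8.3.1 repeats this: the bound is to "be within 7 percentage points of the observed SVR12 rate". No SVR12 rate is attached to that sentence. The next sentence adds that "Once the groups are fixed, the actual lower bound of the 95% confidence interval can be computed".

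The paragraph that follows sets the results beside the SAPPHIRE and PEARL trials, but states that "formal statistical inference comparing results of this study to those of the randomized clinical trials will not be conducted". Section 1.6 hypothesises outcomes like those of the registration trials. Table 1 ("Combined SVR 12 Rates (Intent-to-treat, missing = failure) from Phase 3 Studies by Subpopulation") and sections 1.1 and 1.2 give the rates in those trials.

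**The concern.** The margin of a Wilson interval varies with the observed proportion. At 100 subjects the lower margin ranges from 3.70 points (at 100%) to 9.80 points (at 60%). A statement that the bound will lie within 7 points, conditional only on group size, cannot be true for every observed rate. It is also the only precision figure in the plan.

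The study asks whether real-world results match the trials, and section 1.5 recalls that with interferon regimens they did not. A reader could fairly object that the plan should not quietly presume a high rate when it states its precision. What is at stake is the accuracy of the stated planning precision. If the observed rate were 85% to 91%, the interval would reach further down than the plan led its readers to expect.

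**Working it through.** **Inputs.** Group size n = 100 and the two-sided 95% Wilson score interval come from section 8.3.1, so z = 1.95996 and z² = 3.84146. No continuity correction is mentioned, so none is used. Reference rates come from Table 1 and sections 1.1 and 1.2.

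**Formula.** For an observed proportion p, the lower bound is

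L = [p + z²/(2n) − z·√(p(1−p)/n + z²/(4n²))] / (1 + z²/n),

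and the lower margin is p − L. At n = 100, z²/(2n) = 0.019207, z²/(4n²) = 0.00009604 and 1 + z²/n = 1.038415.

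**Reproducing the plan's figure.** At p = 0.92, the root is √(0.000736 + 0.00009604) = 0.028845. Then L = (0.939207 − 1.95996 × 0.028845) / 1.038415 = 0.85002, and the margin is 6.998 points. The plan's 7 points is met here almost exactly.

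**One step lower.** At p = 0.91, the root is √(0.000819 + 0.00009604) = 0.030250. Then L = (0.929207 − 1.95996 × 0.030250) / 1.038415 = 0.83774, and the margin is 7.23 points.

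| Observed of 100 | Lower bound (%) | Lower margin (points) |
|---|---|---|
| 99 | 94.55 | 4.45 |
| 96 | 90.16 | 5.84 |
| 95 | 88.82 | 6.18 |
| 94 | 87.52 | 6.48 |
| 92 | 85.00 | 6.998 |
| 91 | 83.77 | 7.23 |
| 90 | 82.56 | 7.44 |
| 89 | 81.37 | 7.63 |
| 85 | 76.72 | 8.28 |

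Over all counts from 0 to 100, the 7-point limit is met at 92 to 100 and at 0 to 22. The second range has no relevance here. Read to the nearest whole point, the statement holds from 90 upward.

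**Rates the plan gives reason to expect.** For non-cirrhotic subjects on the regimens used here, Table 1 shows 94.0% to 100% for 1a with ribavirin and 99.0% to 100% for 1b without it. Section 1.1 gives 96.2% and 96.3% for the two SAPPHIRE trials. For treatment-naive 1a subjects with and without ribavirin, section 1.2 reports that rates "for 12 weeks in Study PEARL-IV were 97.0% and 90.2%, respectively"; the first applies to this study. At all the rates for the assigned regimens the margin is 6.48 points or less.

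**Chance of falling outside the condition.** This is the exact binomial probability of 91 or fewer responders among 100, if the true rate equals the trial rate:

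| Assumed true rate | Source | P(91 or fewer) |
|---|---|---|
| 99.0% | 1b naive, no ribavirin | below 0.0001% |
| 97.0% | 1a naive, section 1.2 | 0.3% |
| 95.7% | 1a naive, Table 1 | 2.9% |
| 95.4% | 1a null responders, Table 1 | 4.1% |
| 94.0% | 1a relapsers, Table 1 | 14.6% |

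The last row requires the whole 1a group to have the lowest rate in the table. Missing by more than rounding (89 or fewer) has probability 0.4% at a true 95.7% and 3.8% at 94.0%.

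**Other group sizes.** At an observed 95%, the margin is 7.16 points for 76/80, 6.18 for 95/100 and 5.48 for 114/120. The sentence is expressly limited to 100 per group, so these figures do not contradict it.

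**The case for a change.** The strongest case for an amendment is that the sentence speaks of the observed rate and says the bound *will* be within 7 points, while nothing in that paragraph ties the claim to the trial rates. Even if the true 1a rate equals a trial rate, sampling alone can bring the observed rate below 92%. Rounding moves the boundary to 90% but does not remove it. The plan also intends to set its intervals beside those of the trials, so their width matters to readers. One added clause would make the sentence exact, at almost no cost.

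All of this is correct as a description of the wording, and a sponsor who is revising the section anyway could add the rate. It does not show that anything in the study would come out differently. The group sizes are not derived from the 7 points, no success criterion uses them, and the comparison with the trials is descriptive. A reader of the final report will see the computed bounds, not the planning figure. Nor does the lower margin decide whether a disappointing rate can be told apart from the trial rates. That depends on the upper bound, whose margin stays below 7 points: 90/100 gives an upper bound of 94.5% (4.48 points) and 85/100 gives 90.7% (5.69 points).

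**Conclusion.** The observation is accurate, but no change to the plan is needed. With 100 per group the 7-point statement requires an observed SVR12 of at least 92%, and the plan leaves that condition unsaid. The excess is 0.23 point at 91%, 0.44 at 90% and 1.28 at 85%. At every rate the Background gives for the assigned regimens in non-cirrhotic subjects the statement is true, and section 1.6 makes those rates the natural reading. On those rates the chance of landing below 92% is small for 1a (0.3% to 4.1%, or 14.6% in the extreme case) and negligible for 1b.

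An analyst who follows section 8.3.1 as written obtains the same Wilson intervals and the same descriptive comparison, with or without the extra clause. This conclusion rests on the uncorrected Wilson interval, groups of about 100, and the descriptive purpose stated in the plan. If a decision threshold or a sample-size justification were later built on the 7 points, the assumed rate would have to be stated.
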